### **8.3.2 Investigator reporting: notifying the Penn IRB**

This section describes the requirements for safety reporting by investigators who are Penn faculty, affiliated with a Penn research site, or otherwise responsible for safety reporting to the Penn IRB. The University of Pennsylvania IRB (Penn IRB) requires expedited reporting of those events related to study participation that are unforeseen and indicate that participants or others are at increased risk of harm. The Penn IRB will not acknowledge safety reports or bulk adverse event submissions that do not meet the criteria outlined below. The Penn IRB requires researchers to submit reports of the following problems within 10 working days from the time the investigator becomes aware of the event:

- Any adverse event (regardless of whether the event is serious or non-serious, on-site or off-site) that occurs any time during or after the research study, which in the opinion of the principal investigator is:

Unexpected (An event is “unexpected” when its specificity and severity are not accurately reflected in the protocol-related documents, such as the IRB-approved research protocol, any applicable investigator brochure, and the current IRB-approved informed consent document and other relevant sources of information, such as product labeling and package inserts.)

**AND**

Related to the research procedures (An event is “related to the research procedures” if in the opinion of the principal investigator or sponsor, the event was more likely than not to be caused by the research procedures.)

### **Reporting Process**

Unanticipated problems posing risks to subjects or others as noted above will be reported to the Penn IRB using the form: “Unanticipated Problems Posing Risks to Subjects or Others Including Reportable Adverse Events” or as a written report of the event (including a description of the event with information regarding its fulfillment of the above criteria, follow-up/resolution and need for revision to consent form and/or other study documentation).

Copies of each report and documentation of IRB notification and receipt will be kept in the Clinical Investigator’s study file.

CONFIDENTIAL

This material is the property of the University of Pennsylvania. Do not disclose or use except as authorized in writing by the study sponsor

### **Reporting Deaths: more rapid reporting requirements**

Deaths that occur during the course of a research study and that are:

- Unexpected; AND
- Related to the research study; AND
- When other participants are believed to be at an increased risk of harm

Must be reported to the IRB within 3 days from the time the investigator becomes aware of the death.

### **Other Reportable events:**

For clinical drug trials, the following events are also reportable to the Penn IRB:

- Any adverse experience that, even without detailed analysis, represents a serious unexpected adverse event that is rare in the absence of drug exposure (such as agranulocytosis, hepatic necrosis, Stevens-Johnson syndrome).
- Any adverse event that would cause the sponsor to modify protocol or informed consent form, or would prompt other action by the IRB to assure protection of human subjects.
- Information that indicates a change to the risks or potential benefits of the research, in terms of severity or frequency. For example:
  - An interim analysis indicates that participants have a lower rate of response to treatment than initially expected.
  - Safety monitoring indicates that a particular side effect is more severe, or more frequent than initially expected.
  - A paper is published from another study that shows that an arm of your research study is of no therapeutic value.
- Change in FDA safety labeling or withdrawal from marketing of a drug, device, or biologic used in a research protocol.
- Breach of confidentiality
- Change to the protocol taken without prior IRB review to eliminate apparent immediate hazard to a research participant.
- Incarceration of a participant when the research was not previously approved under Subpart C and the investigator believes it is in the best interest of the subject to remain on the study.
- Complaint of a participant when the complaint indicates unexpected risks or the complaint cannot be resolved by the research team.
- Protocol violation (meaning an accidental or unintentional deviation from the IRB approved protocol) that in the opinion of the investigator placed one or more participants at increased risk, or affects the rights or welfare of subjects.

#### **8.3.3 Sponsor reporting: Notifying the FDA**

The study sponsor is required to report certain study events in an expedited fashion to the FDA. These written notifications of adverse events are referred to as IND safety

CONFIDENTIAL

This material is the property of the University of Pennsylvania. Do not disclose or use except as authorized in writing by the study sponsor

reports. The following describes the safety reporting requirements by timeline for reporting and associated type of event:

- ***Within 7 calendar days***

Any study event that is:

- associated with the use of the study drug
- unexpected,
- fatal or life-threatening, and

- ***Within 15 calendar days***

Any study event that is:

- associated with the use of the study drug,
- unexpected, and
- serious, but not fatal or life-threatening
  - or–
- a previous adverse event that was not initially deemed reportable but is later found to fit the criteria for reporting (reporting within 15 calendar days from when event was deemed reportable).

Any finding from tests in laboratory animals that:

- suggest a significant risk for human subjects including reports of mutagenicity, teratogenicity, or carcinogenicity.

### **Additional reporting requirements**

Sponsors are also required to identify in IND safety reports all previous reports concerning similar adverse events and to analyze the significance of the current event in light of the previous reports.

### **Reporting Process**

Adverse events may be submitted on FDA Form 3500A or in a narrative format. If supplied as in a narrative format, the minimum information to be supplied is noted above at the beginning of section 8.3. The contact information for submitting IND safety reports is noted below:

Contact information pending IND submission

#### **8.4 Unblinding Procedures**

Any intentional breaking of the blind prior to study completion, which may be necessary, for example, in the case of an SAE, will be done in conjunction with the IDS, whose responsibility it will be to notify a designated member of the research team of the individual subject's treatment assignment. Any intentional or unintentional breaking of the blind prior to study completion will be documented and reported to the PI, CTRC, and the IRB within 24 hours and the FDA within seven calendar days.

#### **8.5 Stopping Rules**

The study will be stopped if the following criteria occur:

CONFIDENTIAL

This material is the property of the University of Pennsylvania. Do not disclose or use except as authorized in writing by the study sponsor

1. The PI discovers a condition or conditions that indicate unacceptable risk to the subjects.
2. There is evidence of harm of study-related treatments or procedures to the subjects.

### **8.6 Medical Monitoring**

It is the responsibility of the Principal Investigator to oversee the safety of the study at his/her site. This safety monitoring will include careful assessment and appropriate reporting of adverse events as noted above, as well as the construction and implementation of a site data and safety-monitoring plan (see section 9 Auditing, Monitoring and Inspecting). Medical monitoring will include a regular assessment of the number and type of serious adverse events. Additional medical monitoring will be performed by an external study monitor who is not an investigator in this study.

## **9 Data Handling and Record Keeping**

### **9.1 Confidentiality**

Information about study subjects will be kept confidential and managed according to the requirements of the Health Insurance Portability and Accountability Act of 1996 (HIPAA). Those regulations require a signed subject authorization informing the subject of the following:

- What protected health information (PHI) will be collected from subjects in this study
- Who will have access to that information and why
- Who will use or disclose that information
- The rights of a research subject to revoke their authorization for use of their PHI.

In the event that a subject revokes authorization to collect or use PHI, the investigator, by regulation, retains the ability to use all information collected prior to the revocation of subject authorization. For subjects that have revoked authorization to collect or use PHI, attempts should be made to obtain permission to collect at least vital status (i.e. that the subject is alive) at the end of their scheduled study period.

### **9.2 Source Documents**

Source data is all information, original records of clinical findings, observations, or other activities in a clinical trial necessary for the reconstruction and evaluation of the trial. Source data are contained in source documents. Examples of these original documents, and data records include: hospital records, clinical and office charts, laboratory notes, memoranda, subjects' diaries or evaluation checklists, pharmacy dispensing records, recorded data from automated instruments, copies or transcriptions certified after verification as being accurate and complete, microfiches, photographic negatives, microfilm or magnetic media, x-rays, subject files, and records kept at the pharmacy, at the laboratories, and at medico-technical departments involved in the clinical trial.

### **9.3 Case Report Forms**

The study case report form (CRF) is the primary data collection instrument for the study. All data requested on the CRF must be recorded. All missing data must be explained. If a space on the CRF is left blank because the procedure was not done or the question

CONFIDENTIAL

This material is the property of the University of Pennsylvania. Do not disclose or use except as authorized in writing by the study sponsor

was not asked, write "N/D". If the item is not applicable to the individual case, write "N/A". All entries should be printed legibly in black ink. If any entry error has been made, to correct such an error, draw a single straight line through the incorrect entry and enter the correct data above it. All such changes must be initialed and dated. DO NOT ERASE OR WHITE OUT ERRORS. For clarification of illegible or uncertain entries, print the clarification above the item, then initial and date it.

## 10 Study Monitoring, Auditing, and Inspecting

### 10.1 Study Monitoring Plan

Internal medical monitoring will be performed by [name], who will oversee the safety and validity of the study, according to the University of Pennsylvania Sponsor-Investigator Standard Operating Procedures. In addition, an external medical monitor who is not a study investigator will perform safety monitoring.

Safety monitoring will include careful real-time assessment and appropriate reporting of AEs and SAEs. Safety assessments will be performed by the internal medical monitor after each subject has completed the study (baseline study visit through final visit on treatment 2), and by the external medical monitor after the first, fifteenth, and thirtieth participants have completed the study. All subjects who experiences and/or discontinued due to AEs will be reviewed for key safety data. A final safety assessment will be performed within 3 months of when the last subject has completed the study.

As the Study Sponsor, the PI assumes responsibility to assure that study activities are being carried out as planned so that deficiencies can be identified and corrected. This study will in addition be monitored by a clinical research professional from the staff of Clinical Research Coordinators working for other investigators at the University of Pennsylvania who will be responsible to complete a monitoring process for this study. The designated monitor is not an active member of this study team. A CV for the monitor will be obtained and updated annually. The CV will be kept on file in the Regulatory Binder. The monitor will receive a current protocol, most recently approved Informed Consent Form, and Case Report Forms prior to each monitoring visit.

All CRFs for the first two subjects completed will be 100% source data verified. In addition, CRF's for the 10th, 20th, and 30th subjects will be 100% source data verified upon study completion. If a greater than 10% error rate is noted during the data review, the monitor will source data verify 100% of the data on a larger sample of active subjects following the monitoring visit. The following variables will be 100% source data verified during the monitoring process:

- Informed Consent
- Inclusion/Exclusion Criteria
- Serious and Non-Serious Adverse Events
- Prohibited concomitant medications.
- Drug accountability (IDS will be responsible for drug accountability. Research staff will return all unused study drugs to IDS.

CONFIDENTIAL

This material is the property of the University of Pennsylvania. Do not disclose or use except as authorized in writing by the study sponsor

In addition, all subjects who discontinued for “lost to follow-up” or other reasons will be 100 % source data verified. All monitoring activities completed by the internal study monitor will be recorded on the OHR approved subject review checklists. Monitoring activities cited above will be documented by the monitor in a written report to the PI so that appropriate corrective actions may be implemented as indicated and the report submitted will be filed in the Regulatory Binder.

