### **3 Study Design**

#### **3.1 General Design**

The study design is a randomized, double-blind, cross-over study in which we will examine the pituitary-thyroid axis in older subclinical hypothyroid individuals in response to TRH stimulation and to daily LT4 or LT3 supplementation over a minimum period of 14 consecutive weeks. Physiologic responses to LT4 and LT3 supplementation will also be examined. Thirty participants will receive a total of three TRH stimulation tests and one course each of LT4 and LT3 in randomized order.

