## 7 Statistical Plan

### 7.1 Sample Size Determination

We plan to enroll 30 subjects with an anticipated 15% dropout rate. With an alpha of 0.05 and 80% power and 15% dropout, we will be able to detect a 0.58 standard deviation (SD) change in outcome from baseline. A 3 SD improvement in unstimulated TSH bioactivity has been reported after treatment of overt primary hypothyroidism.[4] No previous studies have measured TSH bioactivity in subclinical hypothyroidism.

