### 7.2 Statistical Methods

All statistical analyses will be performed under consultation with [name], Ph.D., a CTRC biostatistician. Our primary goal will be to assess changes in TRH stimulation test parameters at baseline compared to each thyroid hormone supplementation (LT4 or LT3) and our secondary goal will be to compare physiologic responses to LT4 and LT3 therapy from baseline. The area under the curve (AUC) for TRH-stimulated TSH response will be calculated using the trapezoidal rule. The maximum serum TSH concentration following TRH administration ( $TSH_{max}$ ) will be obtained by direct inspection of the serum concentration-time profiles. Changes in TSH bioactivity, free T4, and total T3 will be determined using the higher of the 120 or 180 minute post-TRH values. Paired t-tests will be used to examine change from baseline for each preparation, and two-tailed tests will be used to compare data between treatment arms. Nonparametric tests will be employed as needed. The primary outcomes will be the changes in TRH stimulation test parameters (AUC,  $TSH_{max}$ ,  $\Delta$  TSH bioactivity,  $\Delta$  free T4,  $\Delta$  total T3). Additional outcomes will include changes in unstimulated TSH bioactivity, REE, body temperature, weight, body composition, lipids, physical actigraphy and heart rate, cognitive testing, symptoms, arterial tonometry, and Doppler echocardiography.

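### The third external safety review waits for a thirtieth completer, which 30 enrolled with 15% expected dropout will almost surely not supply; withdrawals also delay the mid-trial review

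*Combined protocol and SAP*

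**What the plan says.** Section 10.1 (Study Monitoring Plan) sets two medical review schedules in one sentence. The internal monitor reviews "after each subject has completed the study (baseline study visit through final visit on treatment 2". The external monitor's reviews are done "by the external medical monitor after the first, fifteenth, and thirtieth participants have completed the study". The gloss on completion is attached to the internal schedule, but the external clause continues the same sentence with the same verb, so I read it the same way.

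Section 7.1 (Sample Size Determination) states: "We plan to enroll 30 subjects with an anticipated 15% dropout rate". Section 3.1 (General Design) says "Thirty participants will receive a total of three TRH stimulation tests and one course each of LT4 and LT3 in randomized order". Section 4.4 (Early Withdrawal of Subjects) lists reasons for withdrawal before the expected completion date. I find no provision for replacement there or elsewhere.

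Section 10.1 has three further provisions that do not depend on a count of completers: real-time assessment of adverse events, a review of key safety data for participants who have or stop because of adverse events, and a final safety assessment no later than 3 months after the last completion. The last two name no assessor. Section 8.6 gives an external monitor a general role in medical monitoring, without a timetable.

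**The concern.** The last external milestone equals the whole planned enrolment, yet it counts only participants who reach the final visit on the second treatment. One withdrawal without replacement is enough to prevent it. The sample size section expects four or five.

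The same counting rule affects the middle milestone. A participant who leaves early, for whatever reason, does not bring the fifteenth completion closer, so the more dropout there is, the later the mid-trial external review comes.

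At stake is a stated safety commitment in participants aged 70 and over, in a trial where the investigator is also the sponsor. The external monitor's three reviews are the only medical safety reviews with a stated timetable that are assigned to someone outside the investigator team. The estimates of treatment effect are not affected.

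**Working it through.** **Inputs.** Enrolment 30, dropout 15%, alpha 0.05, power 80%, detectable change 0.58 SD (all section 7.1); paired t-tests for change from baseline (section 7.2); external milestones at 1, 15 and 30 completers (section 10.1). Two-sided testing is my assumption, because section 7.2 does not state sidedness for the paired tests.

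**Step 1: how many completers does the plan itself assume?** Section 7.1 states that "we will be able to detect a 0.58 standard deviation (SD) change in outcome from baseline". Expected completers are 30 × 0.85 = 25.5. Solving the noncentral-t power equation of the paired t-test for the detectable change at 80% power gives:

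| Completers | Detectable change (SD) |
|---|---|
| 25 | 0.584 |
| 26 | 0.572 |
| 30 | 0.529 |

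The plan's 0.58 is reproduced at 25 to 26 completers and not at 30. Section 7.1 therefore plans on about 25 to 26 completers, while section 10.1 needs 30.

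**Step 2: chance that the third milestone is reached.** With independent dropout at rate d and no replacement, completers follow Binomial(30, 1 − d), and the milestone requires all 30:

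P(30 of 30) = (1 − d)^30 = 0.85^30 = 0.0076, or 0.8%.

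The chance that it is not reached is 1 − 0.0076 = 99.2%.

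| Dropout rate | P(all 30 complete) |
|---|---|
| 1% | 74% |
| 2% | 55% |
| 5% | 21% |
| 10% | 4.2% |
| 15% (plan) | 0.8% |
| 20% | 0.12% |

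The milestone becomes more likely than not only at about 2% dropout or below.

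**Step 3: would a larger enrolment rescue it?** To expect 30 completers, 30 / 0.85 = 35.3, so 36 would have to be enrolled. Even then P(at least 30 complete) is only 71%.

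**Step 4: the middle milestone.** P(at least 15 of 30 complete) exceeds 0.9999 at 15% dropout, so this review will happen. Its timing is what suffers: 15 / 0.85 = 17.6, so about 17 to 18 participants will have finished, two or three of them by withdrawing (15 × 0.15 / 0.85 = 2.6). This takes withdrawals as spread evenly among the completions.

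**Step 5: after the last dependable milestone.** On expectation 25.5 − 15 = 10.5 participants complete after the fifteenth completion. Of the 30 × 0.15 = 4.5 expected dropouts, some will already have occurred by then, so 4.5 is an upper bound on those that come later.

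**The case against.** The best defence is that the intent is obvious. Thirty is the planned number in the Study Summary, section 3.1 has thirty participants taking both courses, and section 10.1 uses the 30th subject in the same way for case report form checks. On this view thirtieth simply means last, and 15% is a planning allowance, not a forecast. That is plausible as intent, but it does not save the text. Section 10.1 counts those who have completed, section 7.1 enrols 30, and a dropout rate of 5% would still leave only a 21% chance. If the last participant is meant, the sentence should say so.

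Three stronger conclusions are tempting, and the documents do not support them.

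- A reader might infer that withdrawn participants never prompt any review. Section 10.1 provides for review of key safety data when someone stops because of an adverse event, and for source data verification of everyone who discontinues. The second is data checking, not medical review. What is missing is a named reviewer and timing for the first; those who withdraw without an adverse event fall outside it.
- A reader might infer that independent oversight ends at the fifteenth completer. Sections 8.6 and 10.1 give the external monitor a general safety role, section 10.1 adds a data monitor from outside the study team, and sections 8.3.2 and 8.3.3 require IRB and FDA reporting. Only the scheduled external reviews lapse.
- A reader might infer that losing the third review leaves participants on drug unprotected. A review after the thirtieth of 30 completions would come when all treatment has ended. The loss is of an external look back over the whole trial.

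Section 10.1 also does not restrict what each review covers to completers, so participants still on treatment at the fifteenth completion are not necessarily left out of that review.

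**Conclusion.** The concern stands in a limited form. On the plan's own enrolment and dropout, the third scheduled external review has about a 0.8% chance of falling due as written, and the last one that can be relied on is at the fifteenth completion. That middle review is delayed to about 17 to 18 participants finished, because withdrawals do not count. The other safety provisions remain in force, but neither the review of participants who stop because of adverse events nor the final assessment is assigned to the external monitor.

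The figures assume independent dropout at exactly 15% and no replacement; the conflict would ease if dropout were near zero or if enrolment were meant to continue until 30 had completed. This is a rule that does not work as written, not a threat to the trial's validity, and correcting it brings a modest gain.

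**What to change.** In section 10.1, reword the external triggers so that reviews take place after the first and the fifteenth participants have completed or withdrawn, and after the last participant has completed or withdrawn. State that each review covers all participants treated to date, and whether the external monitor performs the final safety assessment.

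This makes the end-of-study external review certain to occur and brings the mid-trial review forward by two or three participants on expectation, so that withdrawals, including those for harm, hasten it. It adds no external milestone between the fifteenth participant and the end, and the last review still follows the end of treatment.

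The cost is an edit of a sentence or two, with the number of scheduled external reviews unchanged at three. One consequence to accept is that the first review may fall on an early withdrawal, with little data; covering everyone treated to date softens this.
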